### **eDiary Rimegepant or Placebo Exposure During Double-Blind Treatment**

eDiary rimegepant or placebo exposure during the DBT phase will be summarized descriptively by treatment group for treated subjects, and will include the following parameters:

- Time on DBT (weeks), derived as (DBT end date – DBT start date + 1)/7
  - Cumulative DB exposure (tablets), derived by summing number of tablets across DB study drug records
  - Average DB exposure (tablets per month), derived as  $4 \times$  cumulative DB exposure/time on DBT
  - Total DB exposure (tablets) summed across all subjects, derived by summing cumulative DB exposure across all subjects
  - Total DB exposure (patient-years), derived by summing (DBT end date – DBT start date + 1)/365.25 across all subjects.
  - Number and percentage of subjects in the following average DB exposure (tablets per month) categories:
    - $> 16.8$  ( $> 20\%$  above EOD dosing)
    - $> 15.4$  ( $> 10\%$  above EOD dosing)
    - $\geq 12.6$  to  $\leq 15.4$  ( $\pm 10\%$  of EOD dosing)
    - $\geq 11.2$  to  $\leq 16.8$  ( $\pm 20\%$  of EOD dosing)
    - $\geq 12.6$  ( $\geq 90\%$  compliant with EOD dosing)
    - $\geq 11.2$  ( $\geq 80\%$  compliant with EOD dosing)
  - Number and percentage of subjects who took  $> 1$  DB tablet on any 1 day. This could be from the same bottle or different bottles due to an unscheduled visit or erroneous eDiary usage.
    - Single study drug record (i.e.,  $\geq 2$  tablets taken from a single source)
    - Multiple study drug records (i.e.,  $\geq 2$  tablets taken based on multiple sources with the same study drug date)
-

- Subject-reported duplicate data (i.e., duplicate study drug times from  $\geq 2$  eDiary subject-reported sources)
  - Subject-reported non-duplicate data (i.e., non-duplicate study drug times from  $\geq 2$  eDiary subject-reported sources)
  - Both site-reported data on medication reconciliation form and subject-reported data (i.e., duplicate study drug dates from the medication reconciliation form and an eDiary subject-reported source)
  - Site-reported data on medication reconciliation form only (i.e., duplicate study drug dates only from the medication reconciliation form)
- Number and percentage of subjects who took:
    - $\geq 12$  DB tablets per month for 3 consecutive months, i.e., 3 consecutive 4-week intervals (see first paragraph below)
    - $\geq 13$ ,  $\geq 14$ ,  $\geq 15$ , and  $\geq 16$  DB tablets per month for 3 consecutive months
  - Number and percentage of subjects who took the incorrect DB study drug:
    - All the time (i.e., as-treated treatment group not equal to as-randomized treatment group)
    - At least once (i.e., subject randomized to rimegepant who took placebo; subject randomized to placebo who took rimegepant).

eDiary rimegepant or placebo exposure during DBT will also be summarized descriptively by subgroup level and overall for all safety subgroups of interest described in Section 6.1.3.2 for each treatment group.

eDiary tablets per month will assess the number of 4-week (28-day) intervals in which a subject exceeded select tablet counts from the DBT start date to the DBT end date, where the number of 4-week intervals are consecutive (see Section 6.3.1.1 for months). For example, suppose a subject takes 20 tablets through 4 weeks, 10 tablets after 4 weeks to 8 weeks, and 25 tablets after 8 weeks to 12 weeks. Thus, this subject is not considered to have taken  $\geq 14$  tablets (more than EOD frequency) per month for 3 consecutive months.

See Section 7.5 for the definition of study days used to define analysis visit windows.

In order to determine subjects who took incorrect DB study drug, eDiary DB study drug dates will be compared to sorted kit dispense dates recorded on the Drug Accountability CRF. Study drug will be considered to be taken from a kit if the kit dispense date  $\leq$  study drug date  $<$  next kit dispense date; if  $> 1$  kit ID has the same dispense date, then study drug will be considered to be taken from the kit with the smallest kit ID. Kit IDs from drug accountability will then be compared to kit IDs in the unblinded container file to determine whether the kit contained DB rimegepant, DB placebo, or OL rimegepant.

A Kaplan-Meier mortality table will summarize time to DBT discontinuation in 4-week intervals (i.e.,  $\leq 4$ ,  $> 4$  to  $\leq 8$ ,  $> 8$  to  $\leq 12$ ,  $> 12$ ) by treatment group and overall for treated subjects. A

---

Kaplan-Meier mortality plot by treatment group will display the percentage of treated subjects on DBT (y-axis) versus weeks (x-axis). Time to DBT discontinuation (weeks) is defined as (DBT end date – DBT start date + 1)/7. Subjects will be considered to have discontinued DBT if they have non-missing DBT last date. Otherwise, in an interim analysis or snapshot before the Week 12 interim analysis database lock, subjects will be censored at the DBT end date.

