[REDACTED]							[REDACTED]
[REDACTED]							[REDACTED]
[REDACTED]							[REDACTED]
Migraine Disability Assessment (MIDAS)				X			X (week 12 only)

¹ Concomitant medications, including prophylactic and standard of care migraine medications, taken during Observation Period and rescue medication taken during the Treatment Phase should be recorded in the subject's paper diary and reviewed by study personnel at each visit. Female subjects will also record menstrual period information on the paper diary which should be reviewed by study personnel at each visit.

² The actual baseline visit date should be used for IWRS enrollment date and eligibility date.

³ Height measured at Screening Visit only. Weight, body temperature, respiratory rate, blood pressure, and heart rate will be collected at all timepoints where indicated. Sitting arterial systolic and diastolic blood pressure and radial artery pulse rate will be measured.

⁴ SAEs, AEs, and Concomitant Procedures must be reported after subject signs informed consent. SAEs should be reported from signing of consent through the 8-week Follow up Safety Visit. Non-serious AEs should be reported from signing of consent through 2-Week Follow up Safety Visit.

⁵ Subjects should finish a bottle of study medication before starting a new bottle. Study drug will be dispensed at monthly (every 4 weeks) study visits, as needed. Unscheduled visits to dispense study medication may be scheduled as needed. At the Week 12 Visit, the open-label study medication will be dispensed and subjects will be instructed not to begin taking rimegepant until confirmation from site staff pending lab results.

⁶ Subjects must take their study medication every other day, regardless of whether or not they have a migraine. Subjects must report each tablet they take in the eDiary. Doses are not required to be taken in the office on days of a study visit, however dosing requirements and compliance should be discussed with subjects at all visits.

⁷ The Observation Period to determine eligibility is 28 days +3 days. The “+3” days window is included for scheduling purposes only. Subjects with less than 24 completed eDiary reports during the Observation Period will not be considered for participation due to non-compliance with the eDiary. Subjects in the Double-blind, Treatment phase who demonstrate poor compliance will be discussed with the Sponsor and corrective training will be completed by the site with the subject.

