4.3.2 Randomized, Double-blind Treatment Phase (12 weeks)

Once completing the Screening/Observational Period, subjects will return to the study site for the Baseline Visit. Subjects who continue to meet all inclusion/exclusion criteria and have been compliant with the eDiary may enter the Treatment Phase, pending review of additional laboratory test results; see Section 4.3.1.1. Because laboratory results from the Randomization (Baseline) Visit will be available after the subject may have been determined to be otherwise eligible for the study, had been randomized, and started treatment, there is the possibility that exclusionary laboratory results from the Randomization Visit may result in early discontinuation from the study.

Subjects will be instructed that they must take one tablet of study drug every other calendar day, regardless of whether they have a migraine on that day or not. If subjects have a migraine during the double-blind phase of the study, if needed, they may treat the migraine with their standard of care medication and continue to take study medication on their regular schedule (scheduled dosing days only).

The electronic subject diary will be completed by subjects to capture dosing of study medication and the frequency and severity of migraines during the Treatment Phase.

Subjects will also use the eDiary to complete the Preference of Medication (PoM) and Satisfaction with Medication (SM) scales. The Migraine-Specific Quality-of-Life Questionnaire v 2.1 (MSQ), the Sheehan Suicidality Tracking Scale (S-STSS), Migraine Assessment Disability (MIDAS) and Clinical Global Impression (CGI-c) will be completed, or administered by the investigator, on paper at specified study visits (Table 1)

Study visits will be approximately every two weeks during the first month and then every 4 weeks, until Week 12 (Table 1). At each visit, the eDiary will be reviewed by site staff for completeness and compliance. Study medication compliance and concomitant medication use and menstrual period information (female subjects) will be reviewed (and compared to the eDiary and paper diary entries, where applicable) and subjects will be dispensed additional study medication as needed. Additional safety (including laboratory tests and ECGs) will be performed per the schedule outlined in Table 1.

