7.2.2 Selection and Timing of Dose and Administration

Study medication (rimegepant or matching placebo) will be assigned via the Rave system. There are no dose adjustments in this study and subjects will receive 30 tablets of rimegepant or placebo in a bottle. Subjects will be dispensed study medication at the Baseline Visit, and the subjects will be instructed that they must take **one tablet every other calendar day, regardless of whether they have a migraine on that day or not**. This is the scheduled dosing regimen for the double-blind treatment phase and the open-label, extension phase.

During the open-label, extension phase, subjects will receive open-label rimegepant. Subjects will be instructed that they must take one tablet every other calendar day, regardless of whether they have a migraine on that day or not. During the open-label, extension phase only, if a subject has a migraine on a non-scheduled dosing day, they may take 1 tablet of rimegepant as acute treatment for their migraine, if needed, with a maximum of one tablet per calendar day. This regimen of scheduled dosing on every other calendar day and as needed rimegepant dosing should be followed for up to 52 weeks in the open-label, extension phase. Subjects can take a maximum of one tablet of study medication per calendar day for 52 weeks during the open-label, extension phase.

Dosing should occur around the same time every other day (EOD) for migraine prevention. It is preferred that subjects dose every other day in the morning, however, it is more important that the subject consistently dose at approximately the same time every other day. The time of dosing should be consistent throughout the study for the EOD dosing days. If the subject has a migraine on a day when they **already took study medication**, the subject can take their rescue medication in accordance with protocol restrictions. Subjects **must** be instructed that they

CANNOT take more than one tablet of study medication every other day during the double-blind, treatment phase. Subjects **must** be instructed to continue taking study medication every other calendar day during the open-label, extension phase. As noted above, subjects may treat a migraine with study medication on a non-scheduled dosing day, but subjects **must** be instructed that during the open-label, extension phase, they **CANNOT** take more than 1 tablet of rimegepant per calendar day.

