7.4 Treatment Compliance

Responsible study personnel will dispense the study drug. Subjects should finish a bottle of study medication before starting a new bottle. Accountability and compliance verification should be documented in the subject's study records.

Subjects must be counseled on the importance of taking the study drug as directed (see Section 7.2.2). Treatment compliance, review of study medication doses reported in the eDiary and through review of returned study medication, should be assessed by site staff at each study visit. Discrepancies between doses reported in the eDiary, review of study medication and information provided by subject must be documented in the source record. Incorrect or missing dosing data and migraine data that are reported in the eDiary will be corrected through either a

Data Clarification Record or a Medication Reconciliation Form. Investigators should inform Subjects that involuntary termination from the study will occur in cases where non-compliance is identified. Study staff should contact a subject in between the monthly study visits if the subject demonstrates non-compliance with the eDiary and document the contact in the source, to identify potential lost to follow up subjects as early as possible.

Investigators must monitor subjects for possible cases of abuse of study medication (subjects taking study drug for non-therapeutic purposes, e.g. for psychoactive effects such as high or euphoria). Investigators should also assess study drug accountability discrepancies (e.g. missing study medication, loss of drug, or non-compliance cases in which more study medication was used, as compared to expected). Investigators should obtain more information and explanation from subjects when there are study drug accountability discrepancies. See Section 8.1.1.

Cases of potential study medication abuse or overdose (including cases of non-compliance with study medication dosing instructions or subjects who discontinue treatment without returning study medication) should be documented in the source record and reported as an AE or SAE as appropriate. Dosing errors (e.g. accidentally taking 2 tablets in one calendar day) should be reported as deviations.

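### SAP 6.2.6.1 credits each double-blind dose to the newest kit dispensed, although the protocol has subjects finish the open bottle first; this can misclassify the probably few subjects given a wrong-content kit

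*SAP*

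**What the plan says.** SAP 6.2.6.1 gives the purpose of the rule: "In order to determine subjects who took incorrect DB study drug, eDiary DB study drug dates will be compared to sorted kit dispense dates" from the Drug Accountability CRF. The rule is "Study drug will be considered to be taken from a kit if the kit dispense date" is on or before the dose date and the dose date is before the next kit's dispense date. If two kits share a dispense date, "then study drug will be considered to be taken from the kit with the smallest kit ID". The kit is then looked up in the unblinded container file to see what it held. Two rows follow: wrong drug at least once, and "All the time (i.e., as-treated treatment group not equal to as-randomized treatment group"). SAP 6.1 and 6.5 tabulate safety by as-treated group. SAP 7.3 also uses that group to set the rimegepant start date.

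The protocol describes how bottles are used. Section 7.4 says "Subjects should finish a bottle of study medication before starting a new bottle", and Table 1 footnote 5 repeats it. Section 7.2.2 says "subjects will receive 30 tablets of rimegepant or placebo in a bottle". Section 4.3.2 says "they must take one tablet of study drug every other calendar day". On supply, footnote 5 says "Study drug will be dispensed at monthly (every 4 weeks) study visits, as needed", and Table 1 marks Baseline and Weeks 4, 8 and 12 as dispensing visits. Section 9.2 analyses safety by randomized treatment if at least one dose of it was received, and otherwise by the treatment actually received.

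**The concern.** The SAP rule treats a new kit as in use from the day it is handed over. The protocol expects the subject to be still using the previous bottle. Nothing in the SAP adjusts for a bottle still open, although SAP 6.2.6.2 already derives tablets used per kit as 30 minus tablets remaining.

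The rule exists to classify subjects whose kits did not all hold the randomized drug, and those are the only subjects it can misclassify. A wrong-content kit that was never opened can be scored as wrong drug taken. Conversely, a subject who took only wrong drug can be scored as having taken both, and so stay in the randomized arm where Protocol 9.2 would move them. For a placebo-randomized subject, that removes double-blind rimegepant exposure from the rimegepant safety data. For a rimegepant-randomized subject, it counts placebo use as rimegepant exposure.

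**Working it through.** **Dosing rate, checked against the SAP.** Every-other-day dosing gives 28/2 = 14 tablets per month. Then 0.9 × 14 = 12.6, 0.8 × 14 = 11.2, 1.1 × 14 = 15.4 and 1.2 × 14 = 16.8. These match the exposure cut-offs in SAP 6.2.6.1.

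**Bottle use.** Assume perfect adherence and a first dose on Day 1. Doses fall on Days 1, 3, …, 83, which is 42 tablets. The first bottle of 30 covers Day 1 to Day 1 + 2 × 29 = Day 59. The second covers the other 12 doses, Days 61 to 83. No third bottle is opened.

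**Doses credited to the wrong kit.** The SAP rule is compared, dose by dose, with finishing each bottle in turn.

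| Kits dispensed | Doses miscredited | Count |
|---|---|---|
| Baseline; Week 8 on Day 56 or 57 | Days 57, 59 | 2 of 42 (4.8%) |
| Baseline; Week 8 on Day 58 or 59 | Day 59 | 1 of 42 (2.4%) |
| Baseline; Week 4 on Day 28 | Days 29 to 59 | 16 of 42 (38.1%) |
| Baseline; Days 28 and 56 | Days 29–55 (14), 57–59 (2), 61–83 (12) | 28 of 42 (66.7%) |
| Baseline; Days 31 and 59 | Days 31–57 (14), 59 (1), 61–83 (12) | 27 of 42 (64.3%) |

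**Effect on classification.** R is a kit with the randomized content and W is one without it, listed in dispense order.

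| Kits and timing | Last dose | Actually taken | SAP result |
|---|---|---|---|
| R, R, W at Baseline, Weeks 4 and 8 | Day 83 | none wrong | wrong at least once |
| W, W, R at Baseline, Weeks 4 and 8 | Day 83 | all wrong | some wrong; stays as randomized |
| R, W at Baseline, Week 4 | e.g. Day 41 | none wrong | wrong at least once |
| W, R at Baseline, Week 4 | e.g. Day 41 | all wrong | some wrong; stays as randomized |
| R, W at Baseline, Week 8 (Day 56) | Day 57 or 59 | none wrong | wrong at least once |
| W, R at Baseline, Week 8 (Day 56) | Day 57 or 59 | all wrong | some wrong; stays as randomized |

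If every kit holds the randomized drug, the classification is right however many doses are credited to the wrong kit. In these cases the as-treated error runs one way: a subject who took only wrong drug is kept in the randomized arm.

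**The case against.** Supply after baseline is as needed. At Week 4 a compliant subject has used 14 of 30 tablets, and the remaining 16 last to Day 59, the end of the Week 8 window (Day 56 + 3). A second bottle is first needed at Week 8, where the rule misplaces only 1 or 2 doses. This stands. A reader might infer from the larger counts that the SAP routinely misplaces 38% or 67% of doses. The documents do not support that, because those counts need kits issued ahead of need. They do not exclude it either, since Table 1 marks both visits for dispensing.

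Table 1 also requires unused medication to be brought back for a compliance check at Weeks 2, 4, 8 and 12. If sites kept the part-used bottle when issuing a new one, the dispense-date rule would be correct. The documents do not say, and the instruction to finish a bottle points the other way. So it cannot be stated as fact that a Week 4 kit is first opened on Day 61.

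The number affected is small. Kits are system-assigned and no mis-dispensing rate is given. An assumed 0 to 1% of 800 is 0 to 8 subjects. For the early-stopping route, the protocol expects 800 − 675 = 125 subjects not to enter the open-label phase. If mis-dispensed subjects leave at that rate, 8 × 125/800 = 1.25 subjects, before the conditions on kit order and timing. A reader might infer that the safety arms are unreliable in general; nothing here supports that.

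Planned listings show kit contents beside eDiary doses and flag differences of 10 or more tablets. They allow affected subjects to be found by eye, but they do not correct the derived classification.

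**Conclusion.** The dispense-date rule conflicts with the protocol's bottle instruction and can misclassify the subjects it is meant to identify. With perfect adherence from Day 1 and bottles finished in order, the miscredited share is 1 or 2 of 42 doses when the second kit comes at Week 8, 16 of 42 when it comes at Week 4, and up to 28 of 42 with kits at both visits.

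A reported result changes only where at least one dispensed kit differs in content from the randomized arm. For those subjects the at-least-once row can be falsely positive, and the all-the-time row can miss a subject, who then sits in the wrong arm of the safety tables. The second effect assumes that as-treated group is derived by this rule. The SAP equates the two and gives no other derivation; the Core SAP was not available.

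As-randomized efficacy, tablet totals and time on double-blind treatment do not use the rule. This is a minor point, worth correcting because the repair is cheap.

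**What to change.** Reconcile the SAP 6.2.6.1 rule with Protocol 7.4. First list subjects with any double-blind kit whose content differs from the randomized arm. If there are none, one sentence in the report closes the matter. For any who exist:

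- Assign eDiary doses to kits in dispense order, crediting each returned kit with 30 minus tablets remaining from the Drug Accountability CRF. Treat a kit returned full as not taken. This also works if a part-used bottle was kept by the site.
- For an unreturned kit, credit only the eDiary doses left after earlier kits are used up, to a maximum of 30 and possibly zero. A flat 30 would score a never-opened, unreturned wrong kit as taken.
- Count wrong drug only if at least one dose is credited to a wrong-content kit.
- Review these subjects individually where eDiary and accountability counts disagree.

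The cost is a SAP wording change, a little programming and a short review. Return counts are imperfect too: Protocol 7.4 expects discrepancies, and SAP 6.2.6.2 tabulates them. SAP Version 10.0 postdates final database lock, and the Week 12 analysis in SAP Section 4 is unblinded, so a change applied now should be reported as made after unblinding.

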A Kaplan-Meier mortality table will summarize time to rimegepant discontinuation in 4-week intervals (i.e.,  $\leq 4$ ,  $> 4$  to  $\leq 8$ , etc.) by treatment group and overall for DB or OL rimegepant treated subjects. A Kaplan-Meier mortality plot (overall, not by treatment group) will display the percentage of DB or OL rimegepant treated subjects on rimegepant (y-axis) versus weeks (x-axis). Time to DB or OL rimegepant discontinuation (weeks) is defined as (DB or OL rimegepant end date – DB or OL rimegepant start date + 1)/7. Subjects will be considered to have discontinued DB or OL rimegepant if they have non-missing DB or OL rimegepant last date. Otherwise, in an interim analysis, subjects will be censored at the DB or OL rimegepant end date.

### **eDiary Study Drug Exposure**

eDiary study drug exposure will be summarized descriptively by treatment group and overall for treated subjects, and will include the following parameters:

- Time in the OP (weeks)
  - Time from randomization to last contact (weeks), where study drug start date will be used if IWRS randomization date is missing
  - Time on DBT (weeks)
  - Cumulative DB exposure (tablets)
  - Average DB exposure (tablets per month)
  - Total DB exposure (tablets) summed across all subjects
  - Time on OL rimegepant (weeks)
  - Cumulative OL rimegepant exposure (tablets)
  - Average OL rimegepant exposure (tablets per month)
  - Total OL rimegepant exposure (tablets) summed across all subjects
  - Time on study drug (weeks), derived as (study drug end date – study drug start date + 1)/7
  - Number and percentage of subjects in the following time on study drug (weeks) categories:  $\geq 11$ ,  $\geq 23$ ,  $\geq 51$ ,  $\geq 63$ . These correspond to using a 1-week lower bound on 3, 6, 12, and 15 months, respectively.
  - Cumulative study drug exposure (tablets), derived by summing number of tablets across study drug records (DBT + OLE)
  - Average study drug exposure (tablets per month), derived as  $4 \times$  cumulative study drug exposure/time on study drug
  - Total study drug exposure (tablets) summed across all subjects, derived by summing cumulative study drug exposure across all subjects
-

- Total study drug exposure (patient-years), derived by summing (study drug end date – study drug start date + 1)/365.25 across all subjects
- Time in follow-up (weeks), derived as derived as (last contact date – study drug last date)/7, for follow-up subjects
- Time on study (weeks), derived as (last contact date – study drug start date + 1)/7
- Number and percentage of subjects in the following time on study (weeks) categories:  $\geq 11$ ,  $\geq 23$ ,  $\geq 51$ ,  $\geq 63$ . These correspond to using a 1-week lower bound on 3, 6, 12, and 15 months, respectively.

Kaplan-Meier mortality tables will summarize time to study drug discontinuation and time to study discontinuation in 4-week intervals (i.e.,  $\leq 4$ ,  $> 4$  to  $\leq 8$ , etc.) by treatment group and overall for treated subjects. A Kaplan-Meier mortality plot by treatment group will display the percentage of treated subjects on study drug (y-axis) versus weeks (x-axis).

- Time to study drug discontinuation (weeks) is defined as (study drug end date – study drug start date + 1)/7. Subjects will be considered to have discontinued study drug if they have non-missing study drug last date/time. Otherwise, in an interim analysis or snapshot before the final database lock, subjects will be censored at the study drug end date.
- Time to study discontinuation (weeks) is defined as (last contact date – IWRS randomization date + 1)/7. If a subject is not randomized, then the study drug start date will be used instead of IWRS randomization date. In an interim analysis or snapshot before the final database lock, subjects will be considered to have discontinued the study if any of the following criteria 1 through 4 are met:
  - 1) All of the following criteria from the DB Subject Status CRF are met (see Section 6.2.3.3):
    - a) Completed or did not complete the DB phase
    - b) Not continuing to OLE phase
    - c) Not continuing to follow-up phase
  - 2) All of the following criteria from the OL Subject Status CRF are met (see Section 6.2.3.4)
    - a) Completed or did not complete the OLE phase
    - b) Not continuing to follow-up phase
  - 3) Did not formally enter the follow-up phase (see Section 6.2.3.5)
  - 4) Completed or did not complete the follow-up phase (see Section 6.2.3.5)Otherwise, subjects will be censored at the last contact date. At the final database lock, all subjects will be considered to have discontinued the study. (This definition of study discontinuation was applied to the CSR.)

